#### **BACKGROUND AND SIGNIFICANCE**

Peripheral pulmonary lesions (PPLs) are often biopsied to assess for the presence of infection, inflammation, or malignancy. Tissue can be acquired in a variety of ways: surgical resection, percutaneous transthoracic needle biopsy, or bronchoscopic biopsy. Bronchoscopy is commonly pursued to determine PPL etiology, with over 500,000 performed annually in the US alone. Advanced imaging and navigational guidance systems are required to accurately approach small peripheral lesions bronchoscopically (1, 2). A variety of navigational technologies are currently available, including electromagnetic navigational bronchoscopy (EMN), virtual bronchoscopy, thin and ultrathin bronchoscopes, and endobronchial ultrasound. No comparative data exist regarding the relative performance of these competing technologies, which are all considered standard of care and currently used interchangeably based on personal preferences and availability (2).

EMN platforms dominate the current navigational bronchoscopy market (2). The largest prospective multicenter study assessing EMN performance showed a diagnostic yield of 73% (3). The more recent addition of intraprocedural digital tomosynthesis has been reported to

increase EMN diagnostic yield to 75-83% (4-6); this feature is included in the ILLUMISITE™ electromagnetic navigational bronchoscopy platform (Medtronic, Minneapolis, MN, U.S.) and is labeled "fluoroscopic navigation".

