# STATISTICAL CONSIDERATIONS

## Sample Size Calculation

EMN diagnostic yield varies widely in the literature (1). Based on data from prior studies and our own published data, we estimated the diagnostic yield of EMN to be 80% (10, 12). The diagnostic yield of SSCB has not been fully elucidated, but published data suggest an overall diagnostic yield of 80% as well (5,7). Assuming the diagnostic yield for EMN is 80%, with a non-inferiority margin set at 10%, cluster size of 2, and no intracluster correlation, we need 202 clusters (OR-days) to have an 80% power to conclude noninferiority at a one-sided type I error rate of 5%, which corresponds to a target of 425 subjects to reach 202 per arm. The noninferiority margin has been chosen based on what would be considered a clinically significant difference (or, put differently, a difference which might influence a hospital to purchase one platform over the other). In case our average cluster size does not reach 2, we will plan to increase the number of clusters to meet our target enrollment of 425 subjects to reach 202 per arm.

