inferiority margin set at 10%, cluster size of 2, and no intracluster correlation, we need 202 clusters (operating days) to have an 80% power to conclude noninferiority at a one-sided type I error rate of 5%, which corresponds to a target of 425 subjects to reach 202 per arm. The noninferiority margin has been chosen based on what would be considered a clinically significant difference (or, put differently, a difference which might influence a hospital to purchase one platform over the other). In case our average cluster size does not reach 2, we will plan to increase the number of clusters to meet our target enrollment of 425 subjects to reach 202 per arm.

Interventions

All patients meeting the eligibility criteria for this study will be enrolled. Cluster randomization will be used, and patients will be assigned to one of the two comparator arms:

a) IonTM Endoluminal System (SSCB)

b) ILLUMISITE[™] Platform (EMN)

Outcomes

Primary Outcome

The primary endpoint will be diagnostic yield, defined as the proportion of procedures that results in acquisition of lesional tissue.

Lesional tissue is defined by the presence of pathological findings that readily explain the presence of a pulmonary lesion. The following common pathological findings are pre-specified:

- Malignancy
- Specific benign pathologic finding including
 - Organizing pneumonia
 - Frank purulence/robust neutrophilic inflammation
 - o Granulomatous inflammation
 - Other specific benign findings such as hamartoma, amyloidoma or other uncommon causes of PPLs with distinctive pathological patterns.

Biopsies not meeting any of the above lesional pathological criteria will be adjudicated as not meeting the primary outcome (not being "diagnostic"), including biopsies with normal lung parenchyma or airway components on biopsy, atypia not diagnostic of malignancy, or non-specific inflammation. A blinded panel will review all non-malignant biopsies at the end of accrual to confirm specific benign or non-diagnostic findings on biopsy. Procedures will be adjudicated as not meeting the primary outcome if the procedure starts but biopsies are not obtained (due to failure to navigate to the lesion, or complication, or equipment failure). A procedure will be considered started at induction of general anesthesia.

Statistical analysis plan for Robotic versus Electromagnetic Bronchoscopy for Pulmonary LesIon AssessmeNT: the RELIANT trial PI: [name]

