The primary analysis for the trial will use an intent-to-treat approach. Participants will be evaluated by treatment group as assigned regardless of what was delivered. All eligible participants will be included.

The primary outcome variable (diagnostic yield) will be compared between groups using a generalized linear mixed model with one-sided test. The primary model will be covariate adjusted, including fixed effects for device assignment, lesion size, density, peripheral location, and bronchus sign, and a random effect for operator. Should the model demonstrate signs of overfitting, covariates may be selected based on priority order (device assignment, lesion size, density, peripheral location, sign, operator).

If non-inferiority is demonstrated, we will proceed with a superiority analysis using the same approach as the non-inferiority analysis, an adjusted generalized linear mixed effects model with the same covariates used in the primary analysis. No adjustment will be made for multiplicity. The superiority analysis would be conducted at a one sided p-value of 0.05.

Secondary and exploratory analysis

A sensitivity analysis using a *per protocol* approach will be conducted to analyze participants based on the device used. We will use the same approach as the primary analysis, an adjusted generalized linear mixed effects model using the same covariates.

The secondary outcome, procedure duration, will be compared between study groups using a linear mixed model. If the procedure duration is skewed, alternative models may be pursued,

Statistical analysis plan for **R**obotic versus Electromagnetic Bronchoscopy for Pulmonary LesIon AssessmeNT: the RELIANT trial PI: [name] such as a cox regression. The primary model will be covariate adjusted following a similar approach to the analysis of the primary outcome. Analysis of the exploratory endpoints will follow a similar approach.

Safety analysis

Procedure complications are expected in usual care, although uncommon. We will report all procedure complications for each device, overall and by type. If event rates exceed 5%, we may proceed with a comparative analysis, which will involve a generalized linear mixed regression model for binary outcomes as specified for the main analysis, with the exception that covariate adjustment may not be possible. The safety analysis dataset will group participants by device used, regardless of assignment.

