All model results will be summarized with point estimates and 95% confidence intervals (CIs), which will be emphasized over p-values when reporting the results for secondary outcomes. No adjustments for multiplicity will be made.

Differential effects

To determine whether differences in outcomes are dependent on baseline characteristics, we will introduce interaction terms into the models developed for the main analysis. Specifically, we will test the interaction between device assignment and the subgrouping variable. Each variable will be tested one by one, such that all main effects but only one interaction term is included at a time. The following putative subgrouping variables are prespecified:

- Nodule size (continuous, treatment effects will be estimated at 1.5cm and 3cm)
- Presence of bronchus sign
- Solid vs subsolid nodule
- Peripheral vs central location Peripheral defined as outer 1/3 of chest

Missingness on the primary or secondary outcome is not expected due to the proximity of its measurement with the procedure and its integration into clinical documentation. Procedures missing the primary outcomes will be considered not diagnostic. Missing covariates will be imputed using multiple imputation with predictive mean matching. There may be missingness on exploratory outcomes. For missing exploratory outcomes, a complete case analysis will be performed.

Statistical analysis plan for Robotic versus Electromagnetic Bronchoscopy for Pulmonary LesIon AssessmeNT: the RELIANT trial

PI: [name]

Diagnostic accuracy

Diagnostic test statistics (e.g., sensitivity, specificity, predictive values, likelihood ratios) will be reported for the two devices. In addition, accuracy of the diagnosis may be modeled using a generalized linear model to explore whether participant or lesion features are predictive of procedure success, as described for the differential effects analysis.

Summary

The results of this study will help to determine whether there is a difference between these two diagnostic bronchoscopy platforms for patient outcomes. The analysis approach we describe is selected based on the trial's pragmatic nature and specifically the intent to understand if the diagnostic yield of the IonTM Endoluminal System (SSCB) is not inferior to the ILLUMISITETM Platform (EMN) in patients undergoing bronchoscopy to biopsy a peripheral lung lesion.

Version and Revision Log

7/12/2022	Version 1: developed with and approved by [name].

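### Does reporting 95% confidence intervals beside a one-sided 5% non-inferiority test call for a change to the SAP?

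*SAP*

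**What the plan says.** Both documents fix the design level. Protocol, Sample Size Calculation: "80% power to conclude noninferiority at a one-sided type I error rate of 5%, which corresponds to a target of 425 subjects". SAP, Sample Size Considerations, uses the same basis: "to have an 80% power to conclude noninferiority at a one-sided type I error rate of 5" per cent.

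SAP, Primary analysis, says diagnostic yield will be "compared between groups using a generalized linear mixed model with one-sided test". It does not repeat the level there. For the step that follows a positive non-inferiority result it does: "The superiority analysis would be conducted at a one sided p-value of 0.05".

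The reporting rule comes after Safety analysis and covers the primary model too: "All model results will be summarized with point estimates and 95% confidence intervals (CIs". The same sentence says of these intervals, "which will be emphasized over p-values when reporting the results for secondary outcomes". Neither document names a 90% interval or a one-sided bound, or gives a rule that compares a confidence limit with the margin.

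**The concern.** A non-inferiority result is commonly read by setting the lower confidence limit against the margin. The interval that matches a one-sided 5% test is the two-sided 90% interval, or equivalently the one-sided 95% lower bound. A two-sided 95% interval matches one-sided 2.5%.

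Followed to the letter, the SAP could therefore produce a valid non-inferiority claim beside an interval that includes a 10-point deficit, or a superiority claim beside an interval that includes zero. Readers might dispute a conclusion that followed the plan. A further worry is that no level stands next to the non-inferiority test in Primary analysis. An analyst might then take the 95% lower limit as the criterion, which would give the trial less power than it was sized for.

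**Working it through.** **Inputs.** Yield 80% on both platforms, margin 10 points, no intracluster correlation, 202 per arm, one-sided 5% (Protocol, Sample Size Calculation and the table after it; SAP, Sample Size Considerations). The table names the Farrington-Manning score test. EMN yields from 73% to 83% are taken from the Protocol's Background and Significance. All figures are for unadjusted proportions; the planned analysis is an adjusted mixed model.

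**1. The plan's own figure.** With the difference held at -10 points, the constrained estimates are 0.7411 and 0.8411.

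- Null SE = √[(0.7411×0.2589 + 0.8411×0.1589)/202] = 0.0401
- SE under 80% v 80% = √(0.32/202) = 0.0398
- Power = Φ[(0.10 − 1.645 × null SE)/SE] = 0.80327 (unrounded inputs)

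This is the table's value. The table's other row, 256 per arm at 0.025, reproduces as 0.80275. The sizing is correct for the level chosen.

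**2. How often test and interval part company.** Exact enumeration of two Binomial(202, p) arms with equal true yield:

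| True yield | Passes at one-sided 5% (Wald) | 95% interval also clears -10 points (Wald) | Gap, Wald | Gap, Farrington-Manning |
|---|---|---|---|---|
| 73% | 73.3% | 62.1% | 11.2% | 11.3% |
| 75% | 75.1% | 64.3% | 10.8% | 10.8% |
| 80% | 80.7% | 71.2% | 9.5% | 9.8% |
| 83% | 84.8% | 76.6% | 8.1% | 9.0% |

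The gap is the power at one-sided 5% minus the power at one-sided 2.5%. Any roughly normal estimate with 80% power at one-sided 5% lies 1.645 + 0.842 = 2.487 SE above the margin. At 2.5% the power is Φ(2.487 − 1.960) = 0.701, so the gap is 0.800 − 0.701 = 0.099. It arises from the pairing of levels and is not peculiar to this trial.

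**3. What one such trial looks like.** SSCB 156/202, EMN 162/202:

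- Difference -2.97 points, SE 4.07 points
- One-sided p = 1 − Φ[(−2.97 + 10)/4.07] = 0.042, so non-inferior
- 95% interval: −2.97 ± 1.960 × 4.07 = −10.95 to 5.01
- 90% lower limit: −2.97 − 1.645 × 4.07 = −9.67

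The 90% limit can be recovered from the reported 95% interval. Its half-width is 7.98, and 7.98 × 1.645/1.960 = 6.70, which gives −2.97 − 6.70 = −9.67.

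**4. Superiority.** With equal platforms at 80%, superiority is declared in 5.07% of trials, and in 2.56% the 95% interval also excludes zero. The discordant share is 5.07 − 2.56 = 2.51% of trials, about half of the declarations. Example: 175/202 v 162/202, +6.44 points, one-sided p = 0.040, 95% interval −0.79 to 13.66.

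**5. Does the plan's error rate move?** At the null (70% v 80%, Wald), the planned one-sided 5% test rejects in 5.0% of trials. Printing a 95% interval beside it leaves that figure as it is. Only if the 95% limit replaced the test would the rate fall to 2.5% and the power to 70.4% (Farrington-Manning). Neither document directs that.

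**The case for a change.** The best case for a change is that it would be cheap. All model results plainly includes the primary model, and no interval matching the primary test is named. Primary analysis gives no level for non-inferiority, so the 95% in the reporting sentence is the only figure in the analysis sections that reaches that result. The Protocol's table treats 0.025 and 0.050 as separate designs, with 256 and 202 per arm. An analyst who took the 95% limit as the rule would be running the 0.025 design at the smaller size.

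The description of the gap stands, and so does the figure of roughly one trial in ten under the design assumptions. The feared misreading has little support in the text. The SAP specifies a test for the primary outcome, gives its level for concluding non-inferiority in its own Sample Size Considerations, and ranks intervals above p-values only for secondary outcomes. If the misreading did occur, it would be conservative: it would cost power, not validity.

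The remedy is also less simple than it looks. The SAP does not say on what scale the adjusted mixed model is set against the margin. A 90% interval written for the difference in yield would settle that scale in passing, and if the test were run on a logit scale the interval need not agree with it.

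**Conclusion.** No change to the plan is needed. The interval level and the test level differ, but they do different jobs: the one-sided 5% test decides, and the 95% interval describes precision. A team that follows the SAP exactly reaches the same conclusion with or without a second interval, and sample size, power and error rates stay as stated.

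The consequence is one of presentation. With equal yields between 73% and 83%, about 8% to 11% of trials would pass the test while the 95% interval includes the margin (9.5% at the design value of 80%, Wald). About 2.5% of trials with equal platforms would declare superiority beside an interval that includes zero. In none of these does the interval make the conclusion wrong.

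This rests on three assumptions: the 95% intervals are two-sided, as is natural but not stated; the one-sided 5% of the sample size text governs the primary test; and unadjusted proportions with no intracluster correlation are a fair guide to the adjusted model. If one-sided intervals were meant, there is no mismatch. Authors who wish to show the 90% limit beside the 95% interval can do so when reporting, since nothing in the SAP prevents it.

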# **PROTOCOL SYNOPSIS**

Title	Robotic versus Electromagnetic Bronchoscopy for Pulmonary
	LesIon AssessmeNT)
Short title	RELIANT
Primary study objective	To compare the diagnostic yield of the Ion TM Endoluminal System (shape sensing catheter bronchoscopy, SSCB) to that of the ILLUMISITE TM Platform (electromagnetic navigational bronchoscopy, EMN) in patients undergoing bronchoscopy with planned biopsy of a peripheral pulmonary lesion.
Study devices	Ion TM Endoluminal System (SSCB); ILLUMISITE TM Platform (EMN).
Design	Single center, open label, pragmatic, non-inferiority, cluster randomized controlled trial.
Study centers	Vanderbilt University Medical Center
Number of clusters	N=202, to be increased if necessary
Inclusion criteria	
 
≥ 18 years of age at time of bronchoscopy.
 
Scheduled for navigational bronchoscopy for the evaluation of a peripheral pulmonary lesion.
 

Exclusion criteria	
 
Enrolled in a different study requiring use of one specific platform
 
Subject declines to participate.
 

Primary endpoint	
 
The primary endpoint will be diagnostic yield obtained from Ion™ or ILLUMISITE™ procedures, defined as the proportion of procedures that result in acquisition of lesional tissue. Lesional tissue: histopathological findings present that readily explain the presence of a pulmonary lesion.
 

Secondary endpoints	1. Duration of the procedure
Exploratory endpoints	
 
Need for additional diagnostic procedures
 
Radiation exposure
 
Diagnostic accuracy at 12-months post-biopsy
 

Safety outcome	
 
Rate of complications (including pneumothorax, bronchopulmonary hemorrhage, respiratory failure, anesthetic complications)
 

Subject follow-up	Patients without malignancy present on biopsy will be followed for up to 12 months as clinically required per standard of care.
Statistical methodology	We assume the diagnostic yield for EMN is 80%. The non-inferiority margin is set at 10%, cluster size of 2, and no intracluster correlation, we need 202 clusters (targeting 425 subjects to reach 202 per arm) to have an 80% power to conclude noninferiority at one-sided type I error rate set at 5%.
Interim analysis	There will be no interim analysis

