# **Study Population**

#### Inclusion Criteria:

- 1.  $\geq$  18 years of age at time of bronchoscopy.
- 2. Undergoing navigational bronchoscopy for biopsy of PPL

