# Endpoints

# Primary Outcome

The primary endpoint will be diagnostic yield, defined as the proportion of procedures that results in acquisition of lesional tissue.

Lesional tissue is defined by the presence of pathological findings that readily explain the presence of a pulmonary lesion. The following common pathological findings are pre-specified:

- Malignancy
- Specific benign pathologic finding including
  - Organizing pneumonia
  - Frank purulence/robust neutrophilic inflammation
  - o Granulomatous inflammation
  - Other specific benign findings such as hamartoma, amyloidoma or other uncommon causes of PPLs with distinctive pathological patterns.

Biopsies not meeting any of the above lesional pathological criteria will be adjudicated as not meeting the primary outcome (not being "diagnostic"), including biopsies with normal lung parenchyma or airway components on biopsy, atypia not diagnostic of malignancy, or non-specific inflammation. A blinded panel will review all non-malignant biopsies at the end of accrual to confirm specific benign or non-diagnostic findings on biopsy. Procedures will be adjudicated as not meeting the primary outcome if the procedure starts but biopsies are not obtained (due to failure to navigate to the lesion, or complication, or equipment failure). A procedure will be considered started at induction of general anesthesia.

Biopsies obtained without the use of EMN or SSCB (e.g., sampling of central lymph nodes using the linear endobronchial ultrasound bronchoscope) will not be included in the diagnostic yield calculations. In case of repeat bronchoscopies, only the index bronchoscopy will be included in the diagnostic yield calculation.

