#### **REGULATORY CONSIDERATIONS**

## **Informed Consent**

We propose a pragmatic, open-label, cluster-randomized trial to compare the diagnostic yield of these standard of care bronchoscopic platforms (EMN vs. SSCB). We will randomly allocate which system (EMN or SSCB) is set-up in each operating room on a given day, and all

peripheral pulmonary lesion biopsies occurring in that room on that day will be performed with the assigned system.

We currently perform advanced diagnostic bronchoscopy in two operating rooms within the main VUMC ORs. We have one EMN system and one SSCB system. Both systems require time to set up, including moving equipment into and out the OR and running calibration steps. OR staff typically arrives one hour before procedures are scheduled to begin each day to set up. Each OR hosts 5-8 bronchoscopies daily, up to four of which on a given day may be EMN/SSCB cases (often back-to-back with each other). Additionally, these procedures need to be planned by the bronchoscopist ahead of time. To accommodate traditional individual patient-level randomization would require moving these platforms between ORs multiple times daily and planning the procedure after consent and enrollment. This would result in a tremendous disruption of our workflow, procedural delay, and suboptimal patient care rendering this study impracticable. Furthermore, about 20% of navigational bronchoscopy cases are performed only after intrathoracic lymph nodes are sampled and negative for malignancy (per rapid on-site cytological examination). Patients with evidence of cancer in their lymph nodes would no longer have an indication for navigational bronchoscopy and would then be excluded after randomization if we were to use traditional individual patient-level randomization, which would significantly impact accrual and power.

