The analysis for the trial will use a intent-to-treat approach. Participants will be evaluated by treatment group as assigned regardless of what was delivered; participants will be excluded if their procedure did not begin, defined as the start of the navigation procedure itself. All eligible participants will be included.

The safety analysis dataset will group participants by device used, regardless of assignment.

Statistical Approach

Our initial analysis will be descriptive in nature, summarizing information that characterizes the cohort and the outcomes. Then, we will proceed with inferential analysis. No interim analyses are planned.

Descriptive Analysis

To characterize the study sample, baseline demographic and clinical data will be described overall and by group. Categorical variables will be described using frequencies and proportions, and continuous variables will be described using means and standard deviations or medians and interquartile ranges, as appropriate. Missingness will be reported for each variable. At a minimum, the following variables will be described at time of enrollment:

- Age (years)
- Gender (male, female, unknown)
- Race (African American, Asian/Pacific Islander, Caucasian, Multiple, Native American, Other, Unknown)
- Ethnicity (Hispanic, Non-Hispanic, Unknown)
- History of cancer (yes/no)
- Smoking History (current, former, never)
- Body mass index (BMI)
- Lesion characteristics
 - o Size (mm)
 - Location (middle vs peripheral)
 - Upper lobe (yes/no)
 - Density (solid, part solid, ground glass opacity)
 - Distance from pleura (cm)
 - Bronchus sign present (yes/no)
- Procedure details

Statistical analysis plan for **R**obotic versus Electromagnetic Bronchoscopy for Pulmonary LesIon AssessmeNT: the RELIANT trial PI: [name]

PI: [name]

- Rapid onsite evaluation (yes/no)
- o Operator
- Digital tomosynthesis (yes/no)
- Cone beam computed tomography (yes/no)
- Biopsy tools

We will describe the outcome variables overall and grouped by study arm using the same approach as for the demographic data. Summary statistics and graphical representations may be displayed, and missingness will be reported for each variable. No statistical comparisons between groups will be done for this descriptive analysis.

Primary analysis

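### The procedure starts at induction in one place and at navigation in another, so the primary analysis set is undetermined for patients anesthetised but never navigated

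*SAP*

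**What the plan says.** **Start of the procedure.** The protocol (Endpoints, Primary Outcome) states: "A procedure will be considered started at induction of general anesthesia". The SAP's Primary Outcome section has the same sentence. Both score a started procedure without biopsies as not diagnostic when the cause is one of three: "due to failure to navigate to the lesion, or complication, or equipment failure". The SAP's Analysis dataset section uses a different start: "participants will be excluded if their procedure did not begin, defined as the start of the navigation procedure itself". The SAP's Primary analysis section restates the intent-to-treat set, with all eligible participants included, and does not repeat that exclusion. The protocol has no such exclusion.

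**Eligibility.** The Protocol Synopsis has "Scheduled for navigational bronchoscopy for the evaluation of a peripheral pulmonary lesion". The protocol's Study Population section has "Undergoing navigational bronchoscopy for biopsy of PPL", and the SAP's Study Population section also uses undergoing.

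**Missing outcomes.** The last paragraph of the SAP's Differential effects section says "Missingness on the primary or secondary outcome is not expected due to the proximity of its measurement with the procedure", and then "Procedures missing the primary outcomes will be considered not diagnostic".

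**Node-first cases.** The protocol's Informed Consent section says "about 20% of navigational bronchoscopy cases are performed only after intrathoracic lymph nodes are sampled and negative for malignancy". It adds that patients with cancer in the nodes lose the indication for navigation, and offers this as a reason against randomising individual patients. Node samples taken without either platform do not count toward yield. Neither document says how a node-positive stop is handled in the analysis.

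**The concern.** A patient can be under anesthesia in an allocated room and never have the lung lesion navigated to. There are two quite different reasons. Either the platform failed or a complication intervened, which bears on the platform comparison, or node sampling removed the need for navigation, which does not.

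Neither start definition separates the two. Starting at navigation removes both kinds of case, including events that the outcome definition counts as failures. Starting at induction keeps both, and the rule for missing outcomes can then turn a node-positive stop into a failure of a platform that was not used.

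The cluster design does not avoid the problem. The room is allocated each morning and consent is taken with procedural consent, so where nodes are sampled in the same session the allocation precedes the node result. In an open-label non-inferiority trial, two analysts could each follow the text and build different primary analysis sets. Failures unrelated to either platform pull a true difference toward zero. Dropping early platform failures can hide a real one.

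**Working it through.** **1. The plan's own figure.** Inputs from the protocol's sample size section: yield 80% in both arms, margin 10 points, one-sided alpha 5%, 202 per arm, no intracluster correlation. The Farrington-Manning score test gives power 0.80327, which is the stated value. The simpler unpooled (Wald) calculation, used below, has SE = √(2 × 0.8 × 0.2 / 202) = 0.0398, so power = Φ(0.10/0.0398 − 1.645) = 0.807, about 81%.

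**2. The texts applied to two kinds of patient, both anesthetised and never navigated.**

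| Governing text | Equipment failure or complication before navigation | Node-positive stop |
|---|---|---|
| SAP Analysis dataset (start of navigation) | Excluded | Excluded |
| Primary Outcome (start at induction) | Non-diagnostic, cause listed | Started; cause not listed; no lung biopsy; the missing-outcome rule may make it non-diagnostic |
| Eligibility: scheduled for | Eligible | Eligible |
| Eligibility: undergoing | Arguable | Arguably not eligible |

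The first two rows disagree on the first kind of patient outright and may disagree on the second.

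**3. Size if the SAP exclusion governs.** Node-positive stops leave the set, dilution is zero, and power stays at 0.803 with 202 analysed per arm. The documents give no rate of equipment failure or complication between induction and navigation, so the effect of losing those cases cannot be computed.

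**4. Size if induction governs and node-positive stops are scored as failures.** Assumptions: 20% of performed navigations follow negative nodes (the protocol's figure); a share q of node-first patients is node-positive (not in the documents; range 10% to 40%); all are stopped after induction; the share is equal in both arms; 202 per arm includes them.

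- Cancelled per performed navigation: r = 0.20 × q/(1 − q)
- Share of inductions: c = r/(1 + r)
- Scored yields: 0.8(1 − c), and 0.7(1 − c) for a platform truly 10 points worse
- Apparent deficit: 10(1 − c) points
- One-sided error: Φ((0.10 − 0.10(1 − c))/SE − 1.645), with SE from the two scored yields
- Power at equal yields: Φ(0.10/SE − 1.645), with both yields at 0.8(1 − c)

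Example, q = 20%: r = 0.20 × 0.25 = 0.05 and c = 0.05/1.05 = 4.8%. The yields are 0.762 and 0.667, and SE = √((0.762 × 0.238 + 0.667 × 0.333)/202) = 0.0447. The error is Φ(0.0048/0.0447 − 1.645) = 0.062.

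| q (assumed) | c | 80% scored as | True 10-point deficit shows as | One-sided error | Power at equal yields |
|---|---|---|---|---|---|
| 0 | 0 | 80% | 10.0 | 5.0% | 81% |
| 10% | 2.2% | 78% | 9.8 | 5.5% | 79% |
| 20% | 4.8% | 76% | 9.5 | 6.2% | 76% |
| 30% | 7.9% | 74% | 9.2 | 7.0% | 74% |
| 40% | 11.8% | 71% | 8.8 | 8.2% | 71% |

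The score test agrees: at c = 5% it gives error 0.063 and power 0.759, and at c = 10% it gives 0.077 and 0.724.

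**The case against.** The strongest reply is that the SAP already deals with node-positive stops. Its Analysis dataset section removes anyone whose navigation did not start, so the missing-outcome rule has nothing to act on. Three other points support this. The failure rule lists three causes, and a lost indication is not one of them. The SAP expects no missing primary outcomes, so its rule reads as a backstop for undocumented results. The Informed Consent section speaks of node-positive patients as exclusions, not failures.

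This stands as the most natural reading, and on it the dilution is zero. A reader might infer that the plan does score these patients as platform failures; the documents do not support that as a settled fact. A reader might also take the 20% as the share lost to malignant nodes. It is the share of cases navigated after negative nodes, and the node-positive share is not given.

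The reply does not remove the contradiction. The same exclusion also drops equipment failures and complications before navigation, which the SAP's outcome section counts as non-diagnostic. The exclusion is absent from the protocol and from the SAP's Primary analysis section, and the synopsis wording would keep a node-positive patient eligible.

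**Conclusion.** The point holds as an unreconciled definition of the primary analysis set, not as a demonstrated bias. For patients anesthetised but never navigated, the documents give two starts and two eligibility wordings, and neither start alone sorts the cases properly.

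Under the SAP exclusion, the cost is the loss of early platform failures, of unknown size. Under induction with the missing-outcome rule, both error rates worsen: one-sided error of about 5.5% to 8.2% in place of 5%, and power of 79% to 71% in place of about 81%. The dilution therefore does not simply favour non-inferiority. It makes a false claim more likely when SSCB is 10 points worse, and a true claim less likely when the yields are equal. These figures rest on an assumed cancelled share of about 2% to 12%, equal in both arms, and on the SAP exclusion not governing.

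This should be settled before the analysis, because it decides who is counted in the primary endpoint.

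**What to change.** Reconcile the protocol's Synopsis, Study Population and Primary Outcome sections with the SAP's Primary Outcome, Analysis dataset, Primary analysis and missing-data text, using one reason-specific rule:

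- After induction, absence of a lung biopsy because of equipment failure, complication or navigation failure counts as non-diagnostic.
- A case in which node results removed the indication before navigation is outside the primary analysis set, is not scored, and is reported by arm in the CONSORT diagram.
- The rule that a missing outcome is non-diagnostic applies only to procedures in the analysis set.
- The eligibility wording is the same in the synopsis and the body.

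The cost is a few sentences and one data field for the reason navigation was not done. The downside is a small post-allocation exclusion, which the counts by arm make visible. If such cases count toward the 425 enrolled, they use up the allowance of 425 − 404 = 21 (21/425 = 4.9%), so the 202 per arm should be counted after the exclusion.
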